8.6.3 Validated Investigator Global Assessment (for subjects with AD only)

For subjects with AD only, disease severity (excluding hands and feet) will be assessed at the visits specified in [Table 1](#), before the study product administration, using the validated Investigator Global Assessment scale for atopic dermatitis (vIGA-AD). The vIGA is a global assessment of the current state of the disease. It is a 5-point morphological assessment of overall disease severity. A detailed description of the vIGA scale is provided in [APPENDIX D](#). The condition will be documented in the eCRF along with the vIGA scores recorded at the visits specified in [Table 1](#).

8.7 Adverse Events and Serious Adverse Events

8.7.1 Definition of Adverse Event

An AE is any untoward medical occurrence in a subject administered a pharmaceutical product and that does not necessarily have a causal relationship with this treatment. An AE can therefore be any unfavorable and unintended sign (including an abnormal laboratory finding), symptom, or disease temporally associated with the use of a study product, whether or not considered related to the study product. AEs and SAEs will be collected from the time of informed consent signature until the final visit / contact.

8.7.2 Definition of Treatment-Emergent Adverse Event

A TEAE is any condition that was not present prior to treatment with the study product but appeared following treatment, was present at treatment initiation but worsened during treatment, or was present at treatment initiation but resolved and then reappeared while the individual was on treatment (regardless of the intensity of the AE when the treatment was initiated).

8.7.3 Definition of Serious Adverse Event

A SAE or reaction is any untoward medical occurrence that, at any dose has any of the following consequences:

- Results in death
- Is life-threatening
- Requires in-patient hospitalization or prolongation of existing hospitalization
- Results in persistent or significant disability/incapacity
- Is a congenital anomaly/birth defect

Note: The term “life-threatening” in the definition of “serious” refers to an event in which the subject was at risk of death at the time of the event; it does not refer to an event that hypothetically might have caused death if it were more severe.

Medical and scientific judgment should be exercised in deciding whether expedited reporting is appropriate in other situations, such as important medical events that may not be immediately life-threatening or result in death or hospitalization, but may jeopardize the subject or may require intervention to prevent one of the other outcomes listed in the definition above. These should also usually be considered serious.

Examples of such events are intensive treatment in an emergency room or at home for allergic bronchospasm, blood dyscrasias, or convulsions that do not result in hospitalization; or development of drug dependency or drug abuse.

8.7.4 Classification of an Adverse Event

8.7.4.1 Relationship to Study Treatment

The investigator will establish causality of the AE to the experimental treatment. The investigator should take into account the subject's history, most recent physical examination findings, and concomitant medications.

The degree of “relatedness” of the AE to the study medication must be described using the following scale:

Not related indicates that there is not a reasonable possibility for relationship of the event to the study medication.

Possibly related indicates that a direct cause and effect relationship between study medication and the AE has not been demonstrated, but there is evidence to suggest there is a reasonable possibility that the event was caused by the study medication.

Probably related indicates that there is evidence suggesting a direct cause and effect relationship between the AE and the study medication.

The statement "**reasonable possibility for relationship**" meaning that there are facts (e.g., evidence such as de-challenge/re-challenge/temporal relationship, exposure, likely cause due to known safety profile, etc.) to suggest a positive causal relationship. The investigators may also change their opinion for causality after follow-up information and may provide a follow-up SAE report with the revised causality assessment.

8.7.4.2 Adverse Event Severity

The intensity of an AE is an estimate of the relative severity of the event made by the investigator based on his or her clinical experience and familiarity with the literature. The following definitions are to be used to rate the severity of an AE:

- **Mild:** The symptom is barely noticeable to the subject and does not influence performance of daily activities. Treatment is not ordinarily indicated.
- **Moderate:** The symptom is sufficiently severe to make the subject uncomfortable, and performance of daily activities is influenced. Treatment may be necessary.
- **Severe:** The symptom causes severe discomfort, and daily activities are significantly impaired or prevented. Treatment may be necessary.

8.7.4.3 Expectedness

The expectedness of each SAE in relation to the study product will be determined by [REDACTED], in consultation with the medical monitor and the sponsor when necessary.

8.7.5 Time Period and Frequency for Event Assessment and Follow-Up

The occurrence of an AE or SAE may come to the attention of study personnel during study visits and interviews of a study subject presenting for medical care, or upon review by a study monitor.

All AEs, including local and systemic reactions, will be captured on the appropriate eCRF. Information to be collected includes event description, date of onset, clinician's assessment of severity, relationship to study product (assessed only by those with the training and authority to make a diagnosis), and date of resolution/stabilization of the event. All AEs occurring while on study must be documented appropriately regardless of relationship.

Before subject enrollment, study site personnel will note the occurrence and nature of each subject's medical condition(s) in the appropriate section of the source document and eCRF. During the study, site personnel will note any change in the condition(s) and the occurrence and nature of any AE.

Any medical condition that is present prior to informed consent signature will be considered as part of medical history and not reported as an AE. However, if the study subject's condition deteriorates after the consent signature, it will be recorded as an AE.

If a subject experiences an AE at any time after the informed consent signature until the end of participation in the study, the event will be recorded as an AE in the source document and eCRF. Any SAE related to the study participation (e.g., screening procedure) will be recorded in the source document and eCRF from the time a subject consents to participate in the study until the end of participation in the study.

The investigator is responsible for appropriate medical care of subjects during the study. The investigator also remains responsible for following through with an appropriate health care option for all AEs that are ongoing at the end of the study. The subject should be followed until the event is resolved or stable. If an AE is ongoing at the end of study, the follow-up duration is left to the discretion of the investigator. Follow-up frequency will be performed at the discretion of the investigator.

Whenever possible, clinically significant abnormal laboratory results are to be reported using the diagnostic that resulted in the clinically significant abnormal laboratory results and not the actual abnormal test.

Worsening of CHE is captured by efficacy assessments and will not be recorded as an AE.

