8.7.7 Serious Adverse Event Reporting

██████████ will be the pharmacovigilance unit responsible for the overall pharmacovigilance process for this study. All SAEs, related to the experimental treatment or not, occurring during the course of the study must be reported on an SAE form to the pharmacovigilance unit (see below contact information) within 24 hours of the knowledge of the occurrence (this refers to any AE that meets one or more of the aforementioned serious criteria). The SAE reporting period ends at the end of the follow-up period or if the subject begins an alternative therapy.

Reporting should be done by sending the completed SAE form to the following e-mail address (faxing can also be done as a second option in case e-mailing is not possible).

Safety Contact Information: ██████████

E-mail: PPD ██████████

Fax: PPD ██████████

The pharmacovigilance unit will inform the primary medical monitor, the sponsor, and Innovaderm within 1 business day of awareness of a new SAE. The pharmacovigilance unit will process and the medical monitor will evaluate all SAEs as soon as the reports are received. For each SAE received, the pharmacovigilance unit, in consultation with the medical monitor if needed, will make a determination as to whether the criteria for expedited reporting to relevant regulatory authorities have been met. The pharmacovigilance unit will manage the expedited reporting of relevant safety information to concerned regulatory agencies in accordance with local laws and regulations.

The study sponsor will be responsible for notifying the Food and Drug Administration (FDA) of any unexpected fatal or life-threatening suspected adverse reactions as soon as possible, but in no case later than 7 calendar days after the sponsor's initial receipt of the information. In addition, the sponsor must notify the FDA and all participating investigators in an Investigational New Drug (IND) safety report of potential serious risks, from clinical trials or any other source, as soon as possible, but in no case later than 15 calendar days after the sponsor determines that the information qualifies for reporting.

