6.2 Handling of Dropouts or Missing data

See Appendix 2 for handling of completely or partially missing dates for prior and concomitant medications and adverse events.

For safety analyses, no imputation of the data will be done and analyses will be conducted on the observed cases (OC). In Part A efficacy analyses will be performed using Mixed Model Repeated Measures (MMRM) analyses as primary analyses to account for missing observations (See section 13.1).

For subjects starting prohibited medications as listed in section 6.4.3 of the protocol, all efficacy data captured after the start of prohibited medication will be considered missing for the analysis of those parameters. A sensitivity analysis on the primary endpoint mTLSS will be done including all efficacy data for these subjects (before and after the prohibited medication).

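### The rule that worsening of chronic hand eczema is not recorded as an adverse event has no exception for serious worsening, and it is not reconciled with the SAE definition

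*Protocol*

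**What the plan says.** Protocol section 8.7.5 closes with an unconditional exemption for the study disease, chronic hand eczema (CHE): "Worsening of CHE is captured by efficacy assessments and will not be recorded as an AE". Neither the protocol nor the SAP qualifies it elsewhere.

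Section 8.7.7 requires all SAEs, related or not, to reach the pharmacovigilance unit within 24 hours, and adds in parentheses: "this refers to any AE that meets one or more of the aforementioned serious criteria".

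Section 8.7.3 defines seriousness without reference to the AE record: "A SAE or reaction is any untoward medical occurrence that, at any dose has any of the following consequences". One listed consequence is "Requires in-patient hospitalization or prolongation of existing hospitalization". The definition does not exclude events of the study disease.

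Two general rules also bear on the point. Section 8.7.2 counts as treatment-emergent a condition that "was present at treatment initiation but worsened during treatment". Section 8.7.5 itself says that if a subject's "condition deteriorates after the consent signature, it will be recorded as an AE".

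**The concern.** Keeping ordinary fluctuation of the study disease out of the AE record is a reasonable choice, because the efficacy scores follow it. The difficulty lies in the serious tail. As written, the exemption covers a mild flare and a hospital admission for hand eczema alike, and the only reason given is that efficacy assessments capture the worsening.

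What is at stake is individual case safety reporting. Without an AE record, a serious worsening on ASN002 might receive no causality assessment (8.7.4.1), no expectedness assessment (8.7.4.3) and no review for expedited reporting (8.7.7). It would also be absent from the TEAE and serious TEAE tables in SAP section 14.1.

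**Working it through.** No arithmetic applies, since the point concerns a reporting rule. The check follows one case, a subject admitted to hospital for worsening hand eczema, through each rule.

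1. **Definition of an SAE (Protocol 8.7.3).** The admission is an untoward occurrence that required hospitalisation. On this section alone it is an SAE.
2. **Recording rule (8.7.5).** The event is worsening of CHE, so it is not recorded as an AE. The sentence sets no limit by severity, seriousness or outcome.
3. **Reporting rule (8.7.7).** All SAEs are to be reported, but the parenthesis describes them as AEs that meet a criterion. A site that has applied step 2 has no AE on file to escalate. Steps 1 and 3 can therefore give different answers, and nothing says which prevails.

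The next question is whether another route would catch the event.

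- **Efficacy scores.** The mTLSS, PGA, HECSI, pain VAS and Extent of Disease (4.1) measure severity and area. None holds seriousness, causality or outcome.
- **Week 18.** The protocol version history says this visit was added for vital signs and AE monitoring. It falls two weeks after placebo subjects switch to ASN002 80 mg. Protocol Table 1 schedules AE evaluation there but none of the efficacy scores. Worsening seen at that visit is not scored and, under 8.7.5, need not be recorded as an AE.
- **Physical examination (8.4.2, 8.4.3).** The dermatological item leaves out hand and foot eczema present at screening and baseline.
- **Duty to alert the sponsor (8.7.6).** This concerns events that seem unusual and sets no deadline. A flare of the disease under study may not seem unusual.
- **Withdrawal for worsening (Protocol section 3; SAP 14.1).** This is a named safety endpoint, summarised at Weeks 4, 8, 12 and 16. Reasons for study discontinuation are tabulated separately for Parts A and B (SAP 7.1). These outputs count withdrawals adequately, but they trigger no 24-hour report and do not show whether the event was serious.

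No other route clearly brings a serious CHE worsening to pharmacovigilance within 24 hours. A neighbouring clause in 8.7.7 should be read with this: "The SAE reporting period ends at the end of the follow-up period or if the subject begins an alternative therapy". The point does not depend on it.

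**The case against.** The strongest answer is that 8.7.5 governs recording only and does not alter the definitions. A CHE admission still fits 8.7.3, and 8.7.7 demands all SAEs, so a careful investigator would report it. This stands in part. It rules out the stronger reading a reader might infer, that serious worsening never reaches pharmacovigilance. The documents support only that it could fail to, because a site following the specific sentence has a textual basis for not reporting.

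It can also be said that a specific exception normally overrides the general rules on deterioration in 8.7.2 and 8.7.5. That is fair for non-serious worsening. The conflict that matters is with 8.7.3, which concerns seriousness.

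Four further inferences are tempting, and the documents do not support them.

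- **Worsening treated with prohibited medication disappears from both the AE tables and the main efficacy analyses.** SAP 6.2 does say that "all efficacy data captured after the start of prohibited medication will be considered missing for the analysis of those parameters", but scores taken before that start stay in the mixed model. Missing hand PGA counts as non-response (SAP 13.2), a sensitivity analysis restores all mTLSS data (SAP 6.2, 13.1), and the number of subjects using prohibited therapy up to Week 16 is tabulated (SAP 7.1).
- **Withdrawal for worsening is uncovered.** It is a safety endpoint to Week 16, and discontinuation reasons are presented for both parts.
- **Weeks 16 to 20 are an unusual gap in efficacy scoring.** Four weeks is the ordinary interval from Week 4 onward, and the scores are also taken at early termination. The narrower point about Week 18 is that an AE-monitoring visit has no scores to which worsening could be referred.
- **TEAE counts are biased in favour of ASN002, or a single SAE would change the safety conclusion.** The exemption applies to every arm, the documents give no basis for a direction, and safety is analysed without inferential statistics (Protocol 9.3.3).

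The exemption also concerns worsening of CHE itself, not complications: serious infection is separately a TEAE of clinical interest in SAP 14.1.

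**Conclusion.** The point holds as an unresolved conflict within the protocol. Section 8.7.5, read with the parenthesis in 8.7.7, lets a site leave a serious worsening of CHE without an AE record, causality assessment or 24-hour SAE report, while 8.7.3 would make the same event an SAE. The reason given for the exemption does not cover serious cases, because efficacy scores hold none of the information that SAE review needs.

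The size cannot be stated as a number. The documents give no rate of CHE worsening that meets a seriousness criterion, and it may be low. About 105 subjects are planned, with 32 weeks of treatment and 4 weeks of follow-up. The conclusion rests on the wording alone and assumes that no document outside the protocol and SAP, such as a study manual, already supplies the exception. The primary endpoint, its analysis and the sample size are not touched. The sponsor should make the change because it concerns safety reporting and costs little.

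**What to change.** Limit the exemption in Protocol 8.7.5 to non-serious worsening, and add a sentence such as: CHE worsening that meets a criterion in section 8.7.3 is recorded as an AE and reported as an SAE under section 8.7.7. The parenthesis in 8.7.7 can then stay, since the event is an AE. Non-serious fluctuation remains with the efficacy scores.

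No further change is needed for withdrawals due to worsening, which existing outputs already count. The SAP tables need no new method, because recorded events would enter the existing TEAE and serious TEAE summaries.

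The cost is a short protocol addition and a memo to sites. The downside is possibly a few more SAE reports.

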8.7.6 Adverse Event Reporting

Investigators are responsible for monitoring the safety of subjects who are participating in this study and for alerting the sponsor to any event that seems unusual, even if this event may be considered an unanticipated benefit to the subject.

8.7.7 Serious Adverse Event Reporting

██████████ will be the pharmacovigilance unit responsible for the overall pharmacovigilance process for this study. All SAEs, related to the experimental treatment or not, occurring during the course of the study must be reported on an SAE form to the pharmacovigilance unit (see below contact information) within 24 hours of the knowledge of the occurrence (this refers to any AE that meets one or more of the aforementioned serious criteria). The SAE reporting period ends at the end of the follow-up period or if the subject begins an alternative therapy.

Reporting should be done by sending the completed SAE form to the following e-mail address (faxing can also be done as a second option in case e-mailing is not possible).

Safety Contact Information: ██████████

E-mail: PPD ██████████

Fax: PPD ██████████

The pharmacovigilance unit will inform the primary medical monitor, the sponsor, and Innovaderm within 1 business day of awareness of a new SAE. The pharmacovigilance unit will process and the medical monitor will evaluate all SAEs as soon as the reports are received. For each SAE received, the pharmacovigilance unit, in consultation with the medical monitor if needed, will make a determination as to whether the criteria for expedited reporting to relevant regulatory authorities have been met. The pharmacovigilance unit will manage the expedited reporting of relevant safety information to concerned regulatory agencies in accordance with local laws and regulations.

The study sponsor will be responsible for notifying the Food and Drug Administration (FDA) of any unexpected fatal or life-threatening suspected adverse reactions as soon as possible, but in no case later than 7 calendar days after the sponsor's initial receipt of the information. In addition, the sponsor must notify the FDA and all participating investigators in an Investigational New Drug (IND) safety report of potential serious risks, from clinical trials or any other source, as soon as possible, but in no case later than 15 calendar days after the sponsor determines that the information qualifies for reporting.

8.7.8 Pregnancy Reporting

If a female subject or a female partner of a male subject becomes pregnant during the study, the subject should inform the study site as soon as possible. Upon confirmation of the pregnancy, the female subject will be discontinued from the study. The investigator must complete a study-specific pregnancy form upon confirmation of a pregnancy and send it to the pharmacovigilance unit within 24 hours of confirmation of the pregnancy (contact information to be used is the same as for SAE reporting). The pharmacovigilance unit will report all cases of pregnancy to the medical monitor, the sponsor, and Innovaderm in a timely manner. Posttreatment follow-up should be done to ensure subject safety. Pregnancy is not itself an AE or SAE; however, maternal/fetal complications or abnormalities will be recorded as AEs or SAEs, as appropriate. The investigator will follow the pregnancy until completion or until pregnancy termination and, in the case of a live-born offspring, to 1 month of age in that infant. The investigator will notify the pharmacovigilance unit and Innovaderm of the outcome as a follow-up to the initial pregnancy form. All pregnancies should be reported to the sponsor and, when applicable, to the ethics committee.

8.7.9 Overdose

Study product overdose is any accidental or intentional use of study product in an amount higher than the dose indicated per protocol for a given subject. Study product compliance (see section 6.3.2) should be reviewed to detect potential instances of overdose (intentional or accidental).

Any study product overdose during the study should be recorded on the source document and eCRF. In the event of overdose, the subject should be closely monitored for any potential AEs. All AEs associated with an overdose should be entered on the Adverse Event eCRF and reported using the procedures detailed in section 8.7.7, SAEs Reporting, even if the events do not meet seriousness criteria. If the AE associated with an overdose does not meet seriousness criteria, it must still be reported using the SAEs reporting procedures and in an expedited manner but should be noted as non-serious on the form and the Adverse Event eCRF. The excess quantity and duration of the overdose should be recorded.

9 STATISTICAL CONSIDERATIONS

9.1 Sample Size Determination

Assuming a common standard deviation of 39% for the percent change-from-baseline mTLSS, a difference of 25% and 35% between the 40 mg dose vs. placebo and the 80 mg dose vs. placebo, respectively, alpha of 5% (two-sided), 25 patients per group would insure an 80% power to obtain a statistically significant treatment effect (using the general F test in an analysis of variance). Assuming between 25-30% dropout rates, up to 35 patients per group will be included in this study.

